1.6.1 Definition of DLT

Reference should be made to the Guidance for Industry Toxicity Grading Scale for Healthy Adult and Adolescent Volunteers Enrolled in Preventive Vaccine Clinical Trials for grading the severity of AEs and laboratory abnormalities where applicable. Based on the known safety profile of entolimod, flu-like symptoms are expected. Decreases in blood pressure, increases in heart rate, hepatic transaminase elevations, hyperglycemia, and hypophosphatemia are expected. DLT will be defined based on the sound clinical judgement of the investigator. DLTs will be considered adverse events and their time and grade severity will be recorded.

These risks and benefits are outlined in the Informed Consent Form and listed in the Investigators Brochure.

2 Study Objectives

Primary Objective

- To evaluate the effect of increasing dose of entolimod on enhancement of the influenza vaccine immunogenicity in the geriatric population (≥ 65 years old).

- To characterize the safety profile of entolimod within the geriatric population (≥ 65 years old) vaccinated against influenza.

Secondary Objectives

- To evaluate the pharmacodynamic effects of entolimod on immunological status, markers of senescence, viscoelasticity of tissue at the injection site, frailty indices and quality of life (QoL).

Exploratory Objectives

- To determine levels of anti-COVID-19 serum-circulating antibodies in a population of confirmed COVID-19 cases
- To determine the rate of the following occurrence in patients that become COVID-19 positive: (i) disease progression requiring hospitalization; (ii) acute respiratory distress syndrome (ARDS); (iii) and 30-day mortality following study drug administration.

3 Study Design

This clinical trial is a randomized, double-blind, placebo-controlled, dose-escalated, single-administration study evaluating the immunogenicity, pharmacodynamics, and safety of entolimod within the geriatric population (≥ 65 years old) vaccinated against influenza. After providing a written informed consent, subjects will undergo screening medical history, physical examination, vital signs, laboratory, and electrocardiogram (ECG) assessments within 28 days prior to study drug administration and influenza vaccination (see figure 2 below).

[figure not shown]

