Subjects will be screened using a questionnaire for potential viral infection of COVID-19 at Day 1 and monthly through the end of the study. Subjects will be asked to provide a nasal swab and serum sample at Day 1 and Month 12. If at any time the subject is evaluated for COVID-19, the study team will document the symptoms, test results and treatment until resolution.

Figure 2. Flowchart of Study Events

NOTE: Subjects will also be contacted every two weeks by phone for Adverse Event monitoring.
Day 7 Safety Assessment will be completed as a remote visit

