- Blood work for pharmacodynamics, vaccine related antibodies, LINE-1, serum antibody testing, and peripheral blood mononuclear cells (PBMCs) prior to vaccine and investigational product administration and 2, 4 and 6 hours post administration
- SAVE procedures (if applicable)

After the observation period (6 hours) and prior to discharge from the Clinical Research and Trials Unit, a reassessment of vital signs including orthostatic blood pressures will be conducted on all study participants.

6.3 Visit 3, Safety Follow-up –Day 1

This visit will be recorded as “Day 1” and will require a visit to the research center where the following tests will be performed:

- Brief physical examination
- Vital signs (orthostatic blood pressure, oxygen saturation, temperature, respiratory rate, weight, and heart rate)
- Review of medications
- Review of adverse events
- Respiratory infection assessment
- Quality of Life (QoL) questionnaire
- ECG
- Blood work – labs [serum chemistry, Hematology, coagulation, cytokines, LINE-1, and vaccine related antibodies]
- Urine collection for urinalysis

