6.4 Visit 4, Safety Follow-up –Day 7 (remote visit)

This visit will be recorded as “Day 7” and will be a remote visit where the following tests will be performed:

- Review of medications
- Review of adverse events
- Respiratory infection assessment
- Quality of Life (QoL) questionnaire

6.5 Visit 5, Follow-up - Month 1

This visit will be recorded as “Month 1” and will require a visit to the research center where the following tests will be performed:

- Vital signs (orthostatic blood pressure, oxygen saturation temperature, respiratory rate, weight, and heart rate)
- Review of medications
- Review of adverse events
- Respiratory infection assessment
- Quality of Life (QoL) questionnaire
- ECG
- Blood work – labs [serum chemistry, Hematology, coagulation, CMV, cytokines, vaccine related antibodies, LINE-1, peripheral blood mononuclear cells (PBMCs) and biomarkers of senescence]
- Urine collection for urinalysis

6.6 Visit 6, Follow-up – Month 2

This visit will be recorded as “Month 2” and will require a visit to the research center where the following tests will be performed:

- Vital signs (orthostatic blood pressure, oxygen saturation temperature, respiratory rate, weight, and heart rate)
- Review of medications
- Review of adverse events
- Respiratory infection assessment
- Quality of Life (QoL) questionnaire
- ECG
- Blood work – labs [serum chemistry, Hematology, coagulation, cytokines, vaccine related antibodies, LINE-1, and peripheral blood mononuclear cells (PBMCs)]
- Urine collection for urinalysis
- Frailty Assessments (includes questionnaires, physical function testing and body composition)

6.7 Visit 7, Follow-up – Month 6

This visit will be recorded as “Month 6” and will require a visit to the research center where the following tests will be performed:

- Vital signs (orthostatic blood pressure, oxygen saturation temperature, respiratory rate, weight, and heart rate)
- Review of medications
- Review of adverse events
- Respiratory infection assessment
- Quality of Life (QoL) questionnaire
- ECG
- Blood work – labs [serum chemistry, Hematology, coagulation, CMV, cytokines, LINE-1, and vaccine related antibodies]
- Urine collection for urinalysis
- Frailty Assessments (includes questionnaires, physical function testing and body composition)

6.8 Visit 8, Follow-up – Month 12

This visit will be recorded as “Month 12” and will require a visit to the research center where the following tests will be performed:

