- Vital signs (orthostatic blood pressure, oxygen saturation, temperature, respiratory rate, weight, and heart rate)
- Review of medications
- Review of adverse events
- Respiratory infection assessment
- Quality of Life (QoL) questionnaire
- COVID-19 Screening questionnaire
- ECG
- Nasal Swab
- Blood work – labs [serum chemistry, Hematology, coagulation, cytokines, and vaccine related antibodies, LINE-1, peripheral blood mononuclear cells (PBMCs) and serum antibody testing]
- Urine collection for urinalysis
- Frailty Assessments (includes questionnaires, physical function testing and body composition)

6.9 Monthly phone visits – Month 3- Month 11

The following tests will be performed remotely (phone visits):

- Review of adverse events
- Review of medications
- Respiratory infection assessment
- COVID-19 Screening questionnaire

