6.15 Adverse Events

Adverse event monitoring will be conducted throughout the study for all subjects. The AE and serious adverse event (SAE) reporting period begins at the time of informed consent and continues through study completion. Adverse events will be assessed at every site and remote visit.

The Investigator will follow-up on all AEs observed or reported by the subject up to the end of the reporting period or until follow-up is no longer necessary. The Investigator will follow-up on SAEs until they are considered resolved or the outcome is known.

Definitions, documentation, and reporting of AEs are described in Section 8. Serious adverse events must be reported within 24 hours as described in Section 8.2.

Table S-1. Schedule of Events

PERIOD	Screening Visit	Treatment Visit	Safety Follow-Up		Monthly Follow-Up					
ON-SITE VISIT	1	2	3	4 (remote)	5	6	-	7	-	8
WEEK	-4	0	Day 1	1						
MONTH					1	2	3 to 5 ^[p]	6	7 to 11 ^[p]	12
Visit Window, week(s)	-28 days			± 1 day	± 1 week					
General Eligibility, Safety, and Frailty Assessments										
Eligibility assessment	X									
Written informed consent	X									
MMSE cognitive status assessment	X									
Frailty assessments ^[a]	X						X	X		X
Brief physical examination ^[b]	X		X							
Medical history	X									
Demographic Information	X									
Vital signs/oxygen saturation/Ht/Wt ^[c]	X ^[q]	X ^{[d][q]}	X ^[q]		X ^[q]	X ^[q]		X ^[q]		X ^[q]
12-lead ECG	X		X		X	X		X		X
AE assessment, including respiratory infection assessment	X	X	X	X	X	X	X	X	X	X
Concomitant medications	X	X	X	X	X	X	X	X	X	X
Quality of life (QoL) questionnaire	X		X	X	X	X	X	X	X	X
Study Drug Administration										
Study drug		X								
Laboratory Assessments										
Serum chemistry ^[e]	X		X		X	X		X		X
Hematology ^[f]	X		X		X	X		X		X
Coagulation ^[g]	X		X		X	X		X		X
Serum virology ^[h]	X									
Urinalysis ^[i]	X		X		X	X		X		X
Serum for entolimod-reactive antibodies ^[j]	X		X		X	X		X		X
Plasma for pharmacodynamics ^[k]		X								
Serum for vaccine related antibodies ^[l]		X			X	X		X		X
Peripheral blood mononuclear cells (PBMC) ^[m]		X			X	X				X
COVID-19, PCR [SARS Coronavirus 2, Molecular Detection, PCR (NP)]		X								X
Exploratory Procedures										
SAVE ^[n]		X								
Biomarkers of senescence ^[o]		X			X			X		X
SARS-CoV-2 IgG Ab [SARS Coronavirus 2 IgG Ab, Serum]		X								X

Footnotes
[a] To be collected at screening, baseline, months 2, 6 and 12 (includes questionnaires, physical function testing, and body composition)

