[b] Physical examination will be limited to cardiac, pulmonary, abdominal, integumentary, and gross neurological evaluation, and to other systems based on specific subject complaints.
[c] Height will only be collected at screening; weight will be collected at all in-person visits
[d] To be collected pre-treatment and 2, 4 and 6 hours post treatment. Wt will only be performed prior to study drug administration.
[e] Serum chemistry studies will include sodium, potassium, chloride, bicarbonate, BUN, creatinine, glucose, calcium, phosphorus, magnesium, total protein, albumin, ALT, AST, ALP, CK, LDH, GGT, total bilirubin, uric acid, and CRP.
[f] Hematology parameters will include hematocrit, hemoglobin, erythrocyte count; absolute counts of leukocytes, neutrophils, lymphocytes, monocytes, eosinophils, basophils; platelet count.
[g] Coagulation studies will include PT and aPTT.
[h] Virology evaluation includes serum CMV, HIV antibody, HBsAg antibody, HBC antibody, HCV antibody. Subjects with a positive antibody evaluation for HBC or HCV should undergo evaluation for HBV DNA and for HCV RNA to determine if the antibody test may be falsely positive. Only CMV testing will be carried out on months 1 and 2.
[i] Urinalysis will include specific gravity, pH, protein, glucose, ketones, bilirubin, urobilinogen, blood, nitrite, leukocyte esterase as assessed by dipstick and microscopic urinalysis evaluating white blood cells, red blood cells, epithelial cells, bacteria, casts, and crystals.
[j] Test will be performed by GPI. Samples may also be used for additional testing related to the study objectives.
[k] G-CSF and IL-6 tests will be performed using the MSD assay platform. Samples are to be collected pre-treatment and 2, 4 and 6 hours post treatment.
[l] Influenza antibody titers A/H1N1, A/H3N2, and B assessed by HAI Assay
[m] Meso Scale Discovery, V-PLEX Proinflammatory panel for 10 cytokine/chemokine mediators of adaptive immune function (IFN- γ , IL-1 β , IL-2, IL-4, IL-6, IL-8, IL-10, IL-12p70, IL-13 and TNF- α) and Interferon gamma ELISPOT assay
[n] Sub-hertz Analysis of ViscoElasticity (SAVE) will be performed 6 hours after study drug administration (or placebo) on left and right deltoid muscles in cohorts receiving entolimod (3 μ g and 10 μ g) and representing a total of 50 subjects.
[o] Blood and urine will be collected for analyses of senescence
[p] Subjects will be contacted bi-weekly via the telephone for remote follow-up visits

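### Subjects infected after dosing have only a Month 12 SARS-CoV-2 IgG level, at an uncontrolled 0 to 12 months after infection, although serum is also drawn at Months 1, 2 and 6

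*Combined protocol and SAP*

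**What the plan says.** The objective, in Section 2 under the exploratory objectives, is "To determine levels of anti-COVID-19 serum-circulating antibodies in a population of confirmed COVID-19 cases". It names no sampling time.

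The sampling schedule is consistent across the document:

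- Section 3: "Subjects will be asked to provide a nasal swab and serum sample at Day 1 and Month 12". Section 3 calls the dosing day Day 1. Section 6.2 calls it Day 0.
- Section 6.2 (dosing day) lists "vaccine related antibodies, LINE-1, serum antibody testing, and peripheral blood mononuclear cells (PBMCs) prior to vaccine", and Section 6.8 (Month 12) lists "peripheral blood mononuclear cells (PBMCs) and serum antibody testing".
- In Table S-1, the row "SARS-CoV-2 IgG Ab [SARS Coronavirus 2 IgG Ab, Serum" is marked only at the treatment visit and Month 12.
- Section 6.5 (Month 1) lists "coagulation, CMV, cytokines, vaccine related antibodies, LINE-1, peripheral blood mononuclear cells (PBMCs) and biomarkers of senescence". It has no SARS-CoV-2 antibody test, and neither do Sections 6.6 and 6.7 (Months 2 and 6).

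For events between the two sampling dates, Section 3 says: "If at any time the subject is evaluated for COVID-19, the study team will document the symptoms, test results and treatment until resolution". This records information but does not call for blood.

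Table S-1 already draws serum at Months 1, 2 and 6 in two rows, one for influenza antibodies and one for entolimod-reactive antibodies. For the second row, footnote [j] says: "Samples may also be used for additional testing related to the study objectives".

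Section 3.6 lists a COVID-19 endpoint based on PCR but none based on antibody level. Section 7.2 refers exploratory endpoints to standard methods in general and does not mention time since infection.

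**The concern.** The level in a case depends on when the sample was taken relative to the infection. Here the sampling date is fixed and the infection date is not. One case may be sampled days after infection and another almost a year after, and the plan treats both as the same quantity.

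The stake is whether this one exploratory objective can be interpreted. With few cases, a summary of Month 12 levels mixes differences in antibody response with differences in timing, and nothing in the plan separates them. Subjects already IgG-positive on the dosing day are not set apart either, so past and new infections could be pooled.

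The primary, secondary and dose-selection analyses do not depend on this measure.

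**Working it through.** The documents give no figure for this objective, so there is nothing to reproduce. The check is the lag from infection to the next serum on which IgG is, or could be, measured.

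**Inputs.** Follow-up is 12 months (Study Summary). IgG is scheduled after dosing at Month 12 only (Section 3, Table S-1). Serum is drawn at Months 1, 2, 6 and 12 (Table S-1). The distribution of infection times is assumed, because the documents give none.

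**Infections uniform over 0 to 12 months**

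- Month 12 only: mean lag = 12/2 = 6.0 months. SD = 12/√12 = 3.46. Share sampled within 3 months = 3/12 = 25%.
- First serum among Months 1, 2, 6 and 12: the intervals are 1, 1, 4 and 6 months wide, with mean lags of 0.5, 0.5, 2 and 3.
  - Mean = (1×0.5 + 1×0.5 + 4×2 + 6×3)/12 = 27/12 = 2.25 months.
  - Mean square = (1³ + 1³ + 4³ + 6³)/(3×12) = 282/36 = 7.83, so SD = √(7.83 − 2.25²) = 1.66.
  - Maximum 6 months. Share within 3 months = (1 + 1 + 3 + 3)/12 = 67%.

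**Range for infection timing.** Mean lag = mean month of next serum − mean month of infection.

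- Early (12 × Beta(1,3), mean month 3): Month 12 only gives 12 − 3 = 9.0. With the interim serum, the chances that the next serum is at Month 1, 2, 6 or 12 are 0.2297, 0.1916, 0.4537 and 0.1250. The mean next-serum month is 4.84 and the mean lag 1.8.
- Late (12 × Beta(3,1), mean month 9): Month 12 only gives 12 − 9 = 3.0. The chances are 0.0006, 0.0041, 0.1204 and 0.8750. The mean next-serum month is 11.23 and the mean lag 2.2.

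**With a minimum lag of 0.5 month (assumed), infections uniform**

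- Infections after month 11.5 have no eligible sample: 0.5/12 = 4%. The rest span 11.5 months.
- Month 12 only: mean = (0.5 + 12)/2 = 6.25 months. Share beyond 6 months = 6/11.5 = 52%.
- With interim serum: mean = (0.5×0.75 + 1×1.0 + 4×2.5 + 6×3.5)/11.5 = 32.375/11.5 = 2.8 months. Share beyond 6 months = 0.5/11.5 = 4%.

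**How much of the spread in levels could be due to time?** This needs a decay rate, so it is only a range. Assume log-linear decline with half-life h. Borrow the influenza CVs of 1.4 and 2.0 from Section 7.1 as a stand-in for between-subject spread. Time variance = (ln 2/h × SD of lag)². Between-subject variance = ln(1 + CV²), which is 1.04² and 1.27². Share due to time:

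| Half-life (months) | CV 1.4, Month 12 only | CV 1.4, interim serum | CV 2.0, Month 12 only | CV 2.0, interim serum |
|---|---|---|---|---|
| 1 | 84% | 55% | 78% | 45% |
| 2 | 57% | 23% | 47% | 17% |
| 3 | 37% | 12% | 28% | 8% |
| 4 | 25% | 7% | 18% | 5% |
| 6 | 13% | 3% | 9% | 2% |

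Under Month 12 sampling, time accounts for more than half only if h is below ln 2 × 3.46/1.04 = 2.3 months (CV 1.4) or ln 2 × 3.46/1.27 = 1.9 months (CV 2.0).

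**The case against.** The strongest reply is that the objective is exploratory and descriptive, that no arm comparison of this level is specified, and that much of what is needed is already collected. COVID-19 questionnaires are monthly and the results of any evaluation are documented, so days since a positive test can be reported without touching the schedule. The dosing-day swab and IgG already identify subjects positive at baseline. This stands. It limits the consequence and makes part of the fix a reporting decision.

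Three further objections also stand:

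- Two sera are tested, not one. The dosing-day serum gives a level for anyone infected earlier, so the point applies only to infections after dosing.
- Leftover volume of the interim serum is not stated. Footnote [j] covers the entolimod-antibody serum, and the influenza-antibody serum carries no such permission.
- The gain depends on when infections occur and is small if they come late. Even with the interim serum, lags run from 0 to 6 months.

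A reader might infer that the Month 12 level mostly reflects time since infection, or that any difference between arms would be a timing artefact. The documents do not support either reading. Both need SARS-CoV-2 antibody decay rates, which are not given, and the table above shows shares from 9% to 84% over plausible-looking assumptions.

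The objection does not remove the central gap. Reporting days since the test describes the spread in timing but does not narrow it, and the plan does not require even that.

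**Conclusion.** The point holds as a modest design improvement. After dosing there is one scheduled IgG level, at an uncontrolled interval of 0 to 12 months after infection, and no rule relates the level to that interval. Levels in confirmed cases are therefore confounded with time since infection, to a degree the documents do not allow one to state.

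With infections assumed uniform, using the interim serum cuts the mean lag by 3.75 months, roughly halves its SD and caps the lag at 6 months. The reduction in the mean is about 7 months if infections come early and under 1 month if late.

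It would go too far to say that the objective cannot be answered. Levels can be measured and described, but Month 12 levels without timing cannot be interpreted reliably. The effect is confined to this exploratory objective.

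**What to change.** 1. For each confirmed case, run the same SARS-CoV-2 IgG assay on the Month 1, 2 and 6 serum drawn under footnote [j], in addition to the dosing-day and Month 12 samples. The sponsor should first confirm that this serum is kept and that enough remains.
2. Define the endpoint as the level in the first sample at or beyond a stated minimum lag after the first positive test. List cases with no eligible sample as such.
3. Report every level with days since the first positive test.
4. Tabulate cases already IgG-positive on the dosing day separately.

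The cost is at most three extra assays per case (15 to 45 at an assumed 5 to 15 cases) and a few sentences in Table S-1 and Section 7.2. No new visit or draw is needed if residual serum suffices. If it does not, report the Month 12 levels by days since the first positive test, which requires only data already documented. Either way the levels will span several months after infection, so the results should be presented as descriptive.

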3.1 General Description

3.2 Number of Subjects

A total of 100 individuals will be randomized into one of four treatment groups (placebo and three progressive dosage entolimod groups).

3.3 Duration of Participation

After consent, for each individual, the duration of participation will be for the length of time required to perform screening plus the 12-month follow-up period after the single-dose administration of entolimod. It is anticipated that the screening will occur within seven days of written content.

3.4 Primary Study Endpoints

Immunogenicity

- Changes of the anti- A/H1N1, anti-A/H3N2, and anti-B influenza virus strains serum circulating antibodies (as assessed using hemagglutination inhibition (HAI) assay) levels.

Safety

- All adverse events (AEs), including dose limiting toxicities (DLTs); laboratory abnormalities; oxygen saturation and vital sign changes, and adverse electrocardiogram (ECG) findings

3.5 Secondary Study Endpoints

Pharmacodynamics and Cellular Immune Responses to Influenza Vaccination

- Time to onset and the number of upper-respiratory infections, including (but not limited to) influenza viral infections (as indicated by subject self-reporting)
- Changes in the concentration of circulating plasma cytokines including (but not limited to): IL-6 and G-CSF as pharmacodynamic indicators of entolimod's activity (measured using MSD assay platform)
- Changes to 10 cytokine/chemokine mediators of adaptive immune function (IFN- γ , IL-1 β , IL-2, IL-4, IL-6, IL-8, IL-10, IL-12p70, IL-13 and TNF- α) in PBMC culture supernatants at 0 and 24 hours after influenza (A/H1N1, A/H3N2 and B) viral stimulation as detected by Meso Scale Discovery, V-PLEX Proinflammatory panel human immunoassay kits.
- Changes in the quantification of IFN γ -positive cells as a marker of cell-mediated immunity (CMI) after vaccination using influenza virus-specific IFN- γ ELISPOT assay kits from R&D Systems.

- Changes in frailty indices and quality of life (QoL) of individuals receiving entolimod versus placebo
- Changes in measures of physical function (6-minute walk test, grip strength) and body composition

